Protocol Title: GO² PEEP Study: The Use of a Bidirectional Oxygenation Valve in the Prevention and Management of Postoperative Atelectasis

Protocol Short Title: GO² PEEP Study

Protocol version 5.0, dated November 20, 2020

NCT Number: NCT04253834

Principal Investigator: [name]
Division of Cardiothoracic Surgery
Emory University School of Medicine
Emory Saint Joseph's Hospital

Sponsor: PEEP Medical, LLC

Protocol Author: [name].
Houston Plastic Craniofacial and Sinus Surgery

Study Objective

The objective of this pilot study is to determine the feasibility and safety of a bidirectional oxygenation mouthpiece compared to incentive spirometry in the prevention and management of postoperative atelectasis.

Hypothesis:

We hypothesize that the bidirectional oxygenation mouthpiece is a safe and effective respiratory therapy, will reduce or prevent postoperative atelectasis, improve oxygenation (PaO₂), improve pulmonary function tests, and reduce postoperative pulmonary complications in cardiac surgical patients compared to conventional incentive spirometry therapy.

Background and Significance

Postoperative pulmonary complications (PPCs) are the principal cause of morbidity, mortality and prolonged hospitalizations in surgical patients,¹⁻³ which results in a 50% increase in healthcare costs compared to postoperative cardiac complications.⁴⁻⁵ This is especially evident following cardiovascular surgery. Pneumonia, unplanned re-intubation and prolonged postoperative mechanical ventilation (>48 hours) remain the most concerning adverse events, with a reported incidence between 2-5%.⁴⁻⁵ One of the most common PPCs is atelectasis, resulting in dyspnea, tachypnea and hypoxemia. A number of identified risk factors associated with the development of PPCs are listed in Table 1.⁶⁻¹⁴

Postoperative atelectasis is a predictable consequence of anesthesia, surgical trauma, and pain associated with breathing.¹⁵ This often results in hypoxemia and pulmonary complications. Methods aimed at increasing lung volume and treating atelectasis, commonly known as *postoperative physiotherapy*, play an important role in preventing PPCs. These methods include cough and deep breathing, continuous positive airway pressure (CPAP), postural drainage, incentive spirometry and positive end expiratory pressure (PEEP).

Introduced by Bartlett *et al*^{2,16} over 40 years ago, incentive spirometry has served as a convenient approach for the postoperative patient to sustain maximal inflations and encourage deep breathing. Minschaert and colleagues found faster recoveries of tidal volumes following conventional protocols of incentive spirometry when compared to conventional physical therapy.¹⁷

Although incentive spirometry is used commonly by post-operative patients, evidence fails to support its benefit.¹⁸⁻²³ One systematic review stated, "Presently, the evidence does not support the use of incentive spirometry for decreasing the incidence of PPCs."¹⁹ Another meta-analysis found no evidence of benefit from incentive spirometry after coronary artery bypass surgery.²² In addition, a recent study on the financial impact of incentive spirometry demonstrated that for the 9.7 million inpatient surgeries performed annually in the United States, the total annual cost of implementing postoperative incentive spirometry is estimated to be \$1.04 billion.²⁴ Most importantly, incentive spirometry is not the ideal treatment for atelectasis or hypoxemia. Incentive spirometry does not provide PEEP.

PEEP is a well-known pulmonary physiologic principle. There are on average 600 million alveoli in the lung. Each alveolus has surfactant to resist the natural propensity for these small air sacs to collapse during exhalation. Despite this surfactant, some alveoli will collapse and not be available for gas exchange. This atelectasis results in a ventilation/perfusion mismatch where alveolar units are perfused but not adequately ventilated. This is referred to as shunting and results in hypoxemia (decreased PaO₂).

Atelectasis, shunting, and hypoxemia are very common complications of surgery and result in significant morbidity and mortality in surgical patients.

PEEP decreases the propensity for the alveoli to collapse by increasing the air pressure in the lungs. This residual pressure in the lungs at the end of exhalation decreases shunting and allows for more complete gas exchange and improved oxygenation. In patients, PEEP is one of the safest ways to increase PaO₂ and is used on almost all modern ventilator settings.

We have developed a simple, comfortable, and straightforward silicone-injected, bidirectional oxygenation mouthpiece that effectively delivers PEEP with every breath (image 1). The purpose of this pilot study is to demonstrate the safety and feasibility of the bidirectional oxygenation mouthpiece in cardiac surgical patients, compare this novel device to conventional incentive spirometry, and identify any potential benefits to respiratory dynamics.

Image 1. Bidirectional oxygenation mouthpiece

1a – PEEP Mouthpiece valve closed during expiration.

1b – PEEP Mouthpiece valve open during inhalation.

Initial testing using the bidirectional oxygenation mouthpiece on healthy subjects has been encouraging. Crouse et al. studied nine subjects during exercise and reported that the “Wearable Positive End-Expiratory Pressure Valve Increases Aerobic Capacity and Performance.”²⁵ Subjects were assigned at random to the novel bidirectional oxygenation mouthpiece, a standard oxygenation mouthpiece, or nothing at all. Subjects wearing the bidirectional oxygenation mouthpiece showed an improvement in VO₂ max of 6.1% compared to the standard mouthpiece and 4.0% compared to no mouthpiece. The endurance test showed an improvement of 6.5% compared to the standard mouthpiece and 6.0% compared to no mouthpiece. All results had p-values < 0.05. No adverse events were reported during the testing. Furthermore, the consumer version of this device, which is being used by athletes during vigorous exercise, has sold over 2000 units to date with no reported adverse events.

Research Design and Methods

Design

This pilot study will utilize a single center, prospective, randomized controlled study design.

Target Study Population

Patients undergoing coronary bypass and/or valve replacement will be evaluated for study eligibility, and will be preoperatively selected according to the below criteria:

Inclusion Criteria

1. Undergoing CABG and/or valve replacement surgery
2. Able to provide written informed consent
3. Maintenance of an arterial line postoperatively

Exclusion Criteria

1. Active smoking, within three months of surgery
2. FEV1 <75% predicted
3. Relative risk to develop pulmonary barotrauma as evident by history of pneumothorax or emphysema
4. Unable or unwilling to provide informed consent, cognitive impairment

Study Endpoints

Primary Endpoint

1. PaO₂ level at 1, 6, 12 and 24 hours post-extubation.

Secondary Endpoints

1. Atelectasis on CXR (Atelectasis Severity Score) immediately post-op and on postoperative days 1-4
2. Oxygen requirement 1, 6, 12 and 24 hours post-extubation and daily each morning
3. CO₂ level at 1, 6, 12 and 24 hours post-extubation
4. FEV1 and FVC measurements pre-op and on postoperative day 3
5. Respiratory rate 1, 6, 12 and 24 hours post-extubation then daily each morning
6. Peak body temperature every 24 hours (as a marker of atelectasis)

Study Procedures

After an eligible patient has provided written informed consent, he/she will be randomly assigned to one of two study cohorts: incentive spirometer (Control Arm) or Bidirectional Oxygenation Valve (G02 Mouthpiece).

Permuted block randomization will be employed to ensure balance between groups when the number of recruited patients reaches a multiple of the block size. All patients will undergo additional postoperative respiratory therapy, including: deep breathing exercises, directed cough, early mobilization and optimal analgesia per routine care. Mouthpieces for each study arm will be provided to a patient throughout the hospitalization.

Both cohorts will use the assigned device following similar protocols:

1. Proper positioning of the patient in bed.
2. Proper positioning of the incentive spirometer or Go2 mouthpiece.
3. A breath cycle will consist of 10 breaths every hour while awake. See instructions in Appendix A.
4. The research assistant will provide adequate training for both devices and will supervise their use.

Arterial blood gases (ABGs) will be collected on 2L/NC (x 5 min) at 1, 6, 12 and 24 post-extubation (+/- 1 hour). Pt. will be asked to use assigned device (incentive spirometer or GO2 mouthpiece) before each ABG is collected. Blood samples will be tested locally at the Emory St. Joseph's Hospital Laboratory.

A chest radiograph will be obtained immediately post-op and daily on post-op days 1-4 to assess the presence of atelectasis using the atelectasis severity score. X-rays will be read by a single radiologist in a blinded fashion.

Respiratory rate will be measured 1, 6, 12 and 24 hours post-extubation then daily each morning.

Body temperature will be measured per nursing routine (as a marker of atelectasis). Temperature max will be recorded each 24 hours.

Schedule of Assessments

Study Procedures	Baseline (up to 30 days before surgery)	Post-Op	POD 1	POD2	POD3	POD4
Consent	X					
Pulmonary function test (PFT)	X				X ²	
Randomization	X					
Treatment: breathing exercises with mouthpieces		X	X	X	X	X
Arterial blood gas (ABGs)			X ¹	X ¹		
Chest x-ray with Atelectasis Severity Score	X	X	X	X	X	X
RR and body temp		X	X	X	X	X
Peak Body Temp			X	X	X	X
Adverse Events		X	X	X	X	X
Use of Device Questionnaire						X ³

¹ABGs 1, 6, 12 and 24 post extubation.

²Performed for research purposes only

³Can be done from POD4 up until discharge from hospital

Statistical Analysis Plan

As a pilot study, our goal is to examine the feasibility and safety of conducting this pilot study on a larger scale. We evaluate the feasibility of recruitment, retention, assessment and implementation of the proposed interventions. We wish to identify any potential flaws in the study design and potential challenges in the subsequent large-scale study. Moreover, the pilot data will give us a first impression of the variability and effect sizes of PaO₂ in the patient population of interest and thus assist in the sample

size and power calculation of the subsequent larger study. Finally, the data that we collect from this pilot will help identify modifications needed in the planning and design of the subsequent study.

We will also assess safety of the new mouthpiece with close monitoring of patient symptoms, physical exam, PaO₂, PCO₂, CXR results, vital signs, and temperature. At the conclusion of the study, we will attempt to assess between-group differences, but given that low power is characteristic of pilot studies, statistical significance is not the focus of the analysis. However, we plan to provide statistical summaries that would be useful in the subsequent study and to other researchers, such as number of patients screened per month, number of patients enrolled per month, proportion of screen eligible who enrolled, lost-to-follow rate, study costs.

We will also summarize patient characteristics at baseline and during follow-up using mean ± standard deviation (or median and interquartile range, as appropriate) for quantitative variables and frequency (percentage) for categorical variables. Summary statistics on PaO₂ will be reported at each measurement occasion for each group. We will also attempt to fit a mixed effects model to examine between-group differences in PaO₂ at each study visit. An error covariance structure most appropriate to the data will be chosen. Every effort will be made to ensure complete follow-up, and to handle missed visits, missingness at random will be assumed. Finally, a qualitative review will also be provided, and this will include, among others, an evaluation of the representativeness of the patient volunteers, a discussion on how to refine the data collection tools, how to improve the database, how to track patients better as well how to improve implementation of the proposed intervention.

Sample Size and Accrual

The sample size for this pilot study will include 20 patients undergoing coronary bypass and/or valve replacement surgery, however, we anticipate that approximately 40 patients may be consented to account for patients that may be ineligible, screen fail, or withdraw from study. This is the number of anticipated eligible patients that may be recruited over a period of 2 months. This number is deemed sufficient to demonstrate the feasibility and safety of the bidirectional oxygenation mouthpiece.

General Design Limitations

Possible pitfalls may include unsupervised use of the assigned mouthpiece or unexpected non-pulmonary complications secondary to the surgery which may affect the results of the analysis. Also, subjects opting out of the study may represent a potential drawback, secondary to pain or fatigue, or evidence of hyperventilation and/or respiratory alkalosis.

Protection of Human Subjects

Institutional Review Board (IRB) Review and Informed Consent

Screening and enrollment will not begin until the Emory University IRB has approved the study protocol and informed consent form.

A physician investigator or study team designee(s) will obtain the informed consent document and verify the date of consent document is within the IRB approval period.

A physician-investigator or study team member designee(s) will begin the informed consent process with the subject ≥24 hours in advance of surgery and/or study procedures when possible. This will allow the subject sufficient opportunity to consider whether or not to participate in a study. The informed consent process may begin either in-person with the patient or by telephone.

The person obtaining informed consent will meet the subject in a private area to present the consent document to the subject, provide a description of the study purpose, procedures, risks/benefits, alternative treatment options, and follow-up schedule. The subject will be given adequate time to fully understand the study, including risks and benefits and study-required follow up visits, and time to ask questions.

If the subject volunteers to participate in a study, he/she must verbalize understanding of the consent before he/she signs. The person obtaining informed consent will obtain all required signatures on the informed consent and HIPAA documents. The subject's consent will be obtained before any research related procedures are performed.

e-Consent

The consent process begins when a patient is screened, identified and verified as eligible for study participation. During the Zoom teleconference call, a member from the study team will discuss the consent form in its entirety with the potential participant. The patient will be offered ample time to discuss the consent form with family and or friends, and have questions answered. In DocuSign, potential subjects have the ability to review the consent document as freely as they would if they were consenting in person. They also have the opportunity to exit the document without signing.

The process for obtaining e-consent is outlined below:

1. First, the IRB approved, stamped consent forms are added to an envelope in DocuSign.
2. Recipients (subject/coordinators) are then added to the envelope and signature and initial fields are assigned to them on the IRB approved consent form.
3. The consent is then sent to the patient via email.
4. Once the consent document is completed by all parties, a signed copy is forwarded to the subject via email. The completed document is also saved on the research team's secure, internal shared drive.

Subject Confidentiality

Subject confidentiality will be guaranteed by storing all data collected in a password-protected database with no associated PHI or patient identifier information included. Patients in this database will only be identified via a unique study ID number. This study ID number will link the electronic data set of each patient to their PHI that will be stored separately in the research study binder.

Subject Safety

Subject safety is of utmost importance throughout this study. The use of oxygenation devices such as the incentive spirometer has not been associated with pulmonary complications or other adverse events. Nonetheless, patients with history of chronic obstructive pulmonary disease or those at risk of developing barotrauma will be excluded from this study.

Adverse Events

Patients will be assessed for the following adverse events:

1. Hypoxia (O₂ saturation <85%)
2. CO rise 20% over baseline
3. Increasing O₂ requirement (non-rebreather mask, biflow, BIPAP requirement)
4. Reintubation

5. Pneumothorax

All serious adverse events will be assessed and reported per the Emory IRB Policies and Procedures.

Data Collection and Monitoring

Study data will be collected from the patient's electronic medical records and from the local Society of Thoracic Surgeons (STS) clinical outcomes database. All information will be entered in a de-identified fashion into a password protected Microsoft Excel spreadsheet created for the study. All study data will be coded using indirect identifiers consisting of a unique numeric study ID code linked to each study participant's name to enable verification of study data against source data, as needed.

Study data, including Protected Health Information (PHI), will be obtained with the patient's direct authorization through the consent form in accordance with HIPAA policy. PHI will be obtained via patient medical records and the STS database as noted above. Permission for use or evaluation of PHI will be limited to the principal investigator, and research study staff. The PHI will be a part of the clinic record and patient study binder. The binders will be kept in a secure location when not being used by the research staff. The PHI collected will be used by the PI and research staff for study tracking purposes, to link and confirm study data with the information located in the patient's clinical record, and if patient safety necessitates, to communicate relevant findings with the patient's healthcare providers. The PHI will be destroyed using the institution's official recycling system once the study is completed. The PI and staff will maintain the records of the study including all correspondence, the study protocol with any/all amendments, all correspondence with and approval from the Emory IRB, and signed informed consent forms in the Regulatory Binder. All these materials, along with individual patient files, data collection forms and source data will be stored and maintained, along with a record of the location of storage, for up to 1 year after the completion of the study. Records will be destroyed using the official institutional recycling system.

Data Management

Upon study completion the final data set will be provided to Sponsor and stored within the secure server in the Houston Plastic Craniofacial and Sinus Surgery office ([name]). All non-identifiable patient data collected will be stored on a password encrypted Microsoft Excel document on the same server. No information will be transmitted electronically outside of the server nor will any data be stored off of the server on any portable type media storage device. All study participant PHI and personal contact information will be securely stored in a study binder at Emory Saint Joseph's research office.

A data safety monitoring plan is not necessary for this minimal risk study.

Facilities

The surgical procedure and postoperative care will take place at Emory Saint Joseph's Hospital, Atlanta, Georgia.

Funding Source

Funding for the study will be provided by PEEP Medical, LLC. Bidirectional oxygenation mouthpieces will be provided by the Sponsor. Incentive spirometers will be provided by the hospital as part of the routine postoperative respiratory therapy.

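### Do the postoperative wording of inclusion criterion 3 and the undefined 20 patients let randomised patients be dropped or replaced?

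*Combined protocol and SAP*

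**What the plan says.** Under Target Study Population, patients are to be "preoperatively selected according to the below criteria". Item 3 of the Inclusion Criteria is "Maintenance of an arterial line postoperatively". Study Procedures then gives the order of events: "After an eligible patient has provided written informed consent, he/she will be randomly assigned to one of two study cohorts". The Schedule of Assessments marks randomisation only in the Baseline column, the same column as consent and the first pulmonary function test; that column reaches back 30 days before surgery. Permuted blocks are used to "ensure balance between groups when the number of recruited patients reaches a multiple of the block size".

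Sample Size and Accrual sets the sample at 20 and adds that "approximately 40 patients may be consented to account for patients that may be ineligible, screen fail, or withdraw from study". It then describes a number of eligible patients expected over 2 months. It gives no loss rate, replacement rule or analysis set.

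The Statistical Analysis Plan names the aims: "We evaluate the feasibility of recruitment, retention, assessment and implementation of the proposed interventions". It promises monthly screening and enrolment counts, the share of eligible patients who enrol, and a loss-to-follow-up rate. PaO2 summaries "will be reported at each measurement occasion for each group", and a mixed effects model is to be attempted, with missed visits treated as missing at random.

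**The concern.** Two features look troublesome together. Whether an arterial line is maintained after surgery cannot be known when the patient is allocated. Taken literally, the criterion would let a randomised patient be declared ineligible after the operation, and the comparison would then no longer be of the groups as randomised.

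The accrual sentence also pools ineligibility and screen failure, which normally come before randomisation, with withdrawal, which may come after it. Consenting extra patients to cover withdrawal hints that withdrawn patients are replaced, so that the 20 might be completers. Retention and recruitment are stated aims of this pilot, and both rates depend on who is counted. PaO2 summaries by arm and time would show how many values exist, but not who was replaced or why a patient left.

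**Working it through.** **1. When criterion 3 is judged.** Three places bear on it. The lead-in to the criteria says that selection is preoperative. Study Procedures randomises a patient who is already eligible and has consented. The schedule puts randomisation at Baseline. All three agree that eligibility is settled before allocation, and under that order criterion 3 can only mean a line that is expected to be kept. Criterion 1, undergoing the operation, looks forward in the same way. No passage provides for removing a randomised patient after surgery.

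**2. The 20 and the 40.** The 20 rests on recruitment, with no alpha, power, effect size or SD, so there is no powered figure to reproduce. The 40 has no stated loss rate. Back-solving gives 1 − 20/40 = 50% combined loss, and 20/(1 − 0.5) = 40. The split before and after randomisation is not given. Let w be the loss after randomisation (an assumption):

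| w | Randomised, if 20 complete: 20/(1 − w), rounded up | Completing, if 20 are randomised: 20(1 − w) |
|---|---|---|
| 0% | 20 | 20 |
| 10% | 23 | 18 |
| 20% | 25 | 16 |
| 30% | 29 | 14 |

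Assume 1:1 allocation and n patients analysed in total at a single time. The 95% half-width for the difference is then t(0.975, n − 2) × √(4/n) SD: 0.94 SD with 20 and 1.07 SD with 16. Both are wide, and neither reading changes what the pilot can conclude about PaO2.

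**3. Retention.** Suppose 4 randomised patients withdraw and are replaced. On randomised patients, retention is 20/24 = 83% (exact 95% CI 63% to 95%). On the final 20 alone it is 20/20 = 100% (83% to 100%). The second figure requires the 4 to vanish from the count, which fits poorly with a plan that commits to reporting loss to follow-up.

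**4. Discarded PaO2 values.** Full data are 20 × 4 = 80 values. If k patients per arm lose the line after the 12-hour sample and are removed altogether, 2 × k × 3 values are lost: 6 (7.5%) for k = 1 and 12 (15%) for k = 2. The standard error √(1/n₁ + 1/n₂) at 1, 6 and 12 hours rises from 0.447 SD (10:10) to 0.471 (9:9, +5%) or 0.500 (8:8, +12%). Under the plan as written, however, such a patient has a missed 24-hour value and three observed ones. A mixed model that assumes missing at random uses the three, and so do the summaries by occasion. The loss is then zero at the first three times.

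**5. Recruitment rate.** The 2-month sentence could give 20/2 = 10 or 40/2 = 20 per month. It speaks of eligible patients, and the 40 is inflated precisely for those who prove ineligible, so 20 is the reading that fits. The sentence after it, which calls the number sufficient, also fits the sample size.

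**6. Block balance.** A 9:11 split gives 0.4495 SD (+0.5%) and 8:12 gives 0.4564 (+2.1%), against 0.4472 at 10:10. This is negligible.

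**The case for a change.** The best argument for a change is that this pilot exists to measure recruitment and retention, so the denominators should be explicit, and a few words would settle them. The missing-at-random sentence covers missing values among patients already included; it does not say who is included or whether anyone is replaced. The General Design Limitations section itself expects patients to opt out through pain or fatigue, so withdrawal during device use is foreseeable.

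This stands as a description of a gap: the 20 are not labelled, no analysis set is named, and reporting of losses by arm and reason is not spelled out. It does not show that following the plan gives a wrong result. Replacement is inferred, since withdrawal may also fall between consent and allocation. A no-replacement rule is a trade-off: it keeps the randomised groups intact, but if some patients yield no PaO2 value the standard error rises by 5% (9:9) or 12% (8:8). A named analysis set would not recover those patients.

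The e-Consent section verifies eligibility before consent, while the accrual text allows for consented patients who prove ineligible. The baseline lung function test explains at least part of this: it shares the Baseline column with consent, and a low FEV1 is an exclusion.

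Subject Safety also says that a history of COPD excludes a patient, while the Exclusion Criteria do not name COPD. Those passages should be reconciled, but they have no bearing on allocation timing or on the meaning of the 20.

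**Conclusion.** No change is needed on this point. Criterion 3 is loosely worded, and the surrounding text fixes its sensible meaning as a planned line judged before allocation. The undefined 20 is a gap that a competent analyst fills in the ordinary way: keep every randomised patient with any PaO2 value in the assigned arm, and compute loss to follow-up on those randomised. The planned model and the promised feasibility counts already point there.

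The figures that make the matter look serious (7.5% or 15% of values discarded, 100% in place of 83% retention, 10 or 20 recruits per month) depend on rules or readings that the plan does not state or that its wording makes unlikely. The loss numbers behind them are illustrations, because the documents give no rates. This conclusion assumes that eligibility is settled before allocation, as the text indicates, and that patients who withdraw are counted in the reported loss rate.

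### Every primary-endpoint blood gas is to be drawn on 2 L/min nasal oxygen, with no exemption or stop rule for a patient who needs more

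*Combined protocol and SAP*

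**What the plan says.** The primary endpoint is PaO₂ at 1, 6, 12 and 24 hours after extubation. Study Procedures sets the sampling condition: "Arterial blood gases (ABGs) will be collected on 2L/NC (x 5 min) at 1, 6, 12 and 24 post-extubation (+/- 1 hour". The condition is stated once, for all patients and all four times.

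Elsewhere the protocol expects oxygen needs to differ between patients at these times:

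- Secondary Endpoints includes "Oxygen requirement 1, 6, 12 and 24 hours post-extubation and daily each morning".
- Adverse Events includes "Increasing O₂ requirement (non-rebreather mask, biflow, BIPAP requirement" and, as a separate item, reintubation.
- The only saturation threshold anywhere is also in that list: "Hypoxia (O₂ saturation <85" percent. It defines an event. It does not govern the blood gas draw.

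The Statistical Analysis Plan gives PaO₂ summaries by group at each time and a mixed effects model, with missed visits assumed missing at random. It states no adjustment for oxygen flow and no rule for a sample taken on anything other than 2 L/min. On the use of the data it says that "the pilot data will give us a first impression of the variability and effect sizes of PaO₂ in the patient population of interest", to help size a larger study.

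**The concern.** A fixed oxygen condition is a sound way to make PaO₂ comparable between patients and times. The gap is the patient who cannot safely be put on that condition. The protocol leaves staff two courses.

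1. **Follow the text.** A patient on higher support is reduced to 2 L/min for five minutes, up to four times, for a protocol-timed sample. No written limit says when not to start or when to stop. In a study whose objective includes safety, a desaturation brought on by the sampling could also be counted as an adverse event during device use.
2. **Use bedside judgement and decline.** The PaO₂ is then not taken, or is taken on other oxygen. In either case the reason is poor oxygenation, which is what PaO₂ measures. The plan has no rule for recording or analysing such a draw.

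At stake are patient safety during a research procedure and, to a lesser degree, the PaO₂ mean and SD carried into the next trial.

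**Working it through.** **Is there a rule anywhere?** I looked in each section where one could stand.

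| Section | What it supplies | Does it govern the 2 L/min draw? |
|---|---|---|
| Study Procedures | Flow, duration, times, window, device use beforehand | Sets the condition; no exception |
| Exclusion Criteria | FEV1 below 75% predicted, recent smoking, history of pneumothorax or emphysema | Lowers risk, but acts before surgery |
| Adverse Events | Saturation below 85%, rising oxygen need, reintubation | Classifies an event once it has occurred |
| Statistical Analysis Plan | Close monitoring of symptoms, PaO₂ and vital signs | Detects; does not prevent |
| Statistical Analysis Plan | Missing at random for missed visits | Does not address draws on other oxygen |

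No section gives an exemption, a stop rule or a handling rule.

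**How often?** The documents do not say. For an assumed proportion p of patients needing more than 2 L/min, the expected number in 20 is 20p, and the chance of at least one is 1 − (1 − p)²⁰.

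| Assumed p | Expected patients | Chance of at least one |
|---|---|---|
| 5% | 1 | 64% |
| 10% | 2 | 88% |
| 20% | 4 | 99% |
| 30% | 6 | 99.9% |

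**How large is the statistical effect?** The plan has no power calculation to reproduce; it gives 20 patients and no SD. Assumptions, none from the documents: 10 per arm, normal PaO₂ in SD units, no true effect.

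*Near-worst case, the lowest values missing in one arm only.* The expected lowest of 10 normal values is −1.539 and the second lowest −1.001.

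- One missing: shift in the visit mean = 1.539/9 = 0.17 SD; SE of the difference = √(1/10 + 1/9) = 0.46 SD.
- Two missing: shift = (1.539 + 1.001)/8 = 0.32 SD; SE = √(1/10 + 1/8) = 0.47 SD.

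*Mixed model with the patient's other three draws observed.* With equal correlation ρ between visits and known covariance, the other draws recover a share 3ρ²/(1 + 2ρ) of the shift, whichever visit is affected. The remaining shift is:

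| ρ | 1 − 3ρ²/(1 + 2ρ) | One missing | Two missing |
|---|---|---|---|
| 0.3 | 0.831 | 0.14 SD | 0.26 SD |
| 0.5 | 0.625 | 0.11 SD | 0.20 SD |
| 0.7 | 0.388 | 0.07 SD | 0.12 SD |

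*Milder case, one or two missing at random from the lower five.* The mean of the expected lower five is −0.739. The shift is 0.739/9 = 0.08 SD or 2 × 0.739/8 = 0.18 SD. The variance is almost unchanged (1.00 or 0.98 of its true value, by simulation).

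*Variance for the next trial.* By simulation, losing the lowest value leaves an arm's variance at 0.76 of its true value, and losing the lowest two at 0.63. A trial sized for 80% power on variance ratio v has power Φ(√v × 2.802 − 1.960).

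- Lowest one lost in one arm only: pooled v = (8 × 0.763 + 9 × 1)/17 = 0.89; power about 75%.
- Lowest one lost in both arms: v = 0.763; power about 69%.
- Lowest two lost in both arms: v = 0.629; power about 60%.

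For scale, a variance on 18 degrees of freedom has a relative SE of √(2/18) = 33%.

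**The case against.** The strongest reply is that this is a clarification. The documents give no frequency of need above 2 L/min and no risk of desaturation over five minutes. Patients have an arterial line, those with poor baseline lung function are excluded, monitoring is close, and nothing in the protocol overrides bedside care. Oxygen requirement is recorded at the same four times and escalation is an adverse event, so most affected patients could be identified afterwards. Finding design flaws is also a stated aim of the pilot.

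Much of this stands. The safety consequence is a possibility that the text allows, not a harm it shows. But the mitigations either act before surgery, detect an event after it starts, or rely on staff departing from the written procedure. None is a rule for the draw. Oxygen requirement at a given hour is also not the same as the oxygen in use when the sample was taken.

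A reader might infer four stronger things that the documents do not support.

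- **That values taken on higher oxygen will be pooled with the rest.** No section says so. A draw on another flow departs from the stated condition, and the plan is silent on what follows.
- **That the waiver in Data Management, "A data safety monitoring plan is not necessary for this minimal risk study", shows that a stop rule was rejected.** Such a plan need not contain a bedside rule for a blood gas, so its absence shows little.
- **That Background and Significance gives the frequency.** "Atelectasis, shunting, and hypoxemia are very common complications of surgery" concerns surgery in general. "Pneumonia, unplanned re-intubation and prolonged postoperative mechanical ventilation (>48 hours) remain the most concerning adverse events, with a reported incidence between 2-5" percent covers different events. Prolonged initial ventilation precedes extubation, and the figure has no 24-hour limit.
- **That the next trial would be seriously underpowered.** The 69% and 60% figures need the lowest values lost in both arms, that is 2 or 4 of 20 patients.

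**Conclusion.** The concern holds in a limited form. The protocol states a sampling rule that, followed as written, lowers oxygen for a patient who needs more, and it foresees such patients without providing for them. If staff do not follow the rule, the affected values are missing or not comparable for a reason linked to the outcome, and missing at random is doubtful for those draws.

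The safety point carries the recommendation, and its frequency and size cannot be estimated from the documents. The statistical effect alone is modest. Even the near-worst-case shift of 0.17 to 0.32 SD is below the standard error, the mixed model reduces it to 0.07 to 0.26 SD, and the plan says that significance is not its focus. Any loss of variance is at most about the size of sampling noise, though it runs in one direction. These figures rest on 10 per arm, normal values and an assumed pattern of loss. The change should be made because it is cheap and concerns patient safety, not because the PaO₂ results would otherwise be unusable.

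**What to change.** **In Study Procedures**, add that the step-down to 2 L/min is not attempted in a patient on support above a stated limit (for example non-rebreather, biflow or BIPAP), and is stopped if saturation falls below a stated floor. The investigators should set both limits, with the floor well above the 85% that defines the adverse event.

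**At each blood gas**, record the oxygen device and flow actually in use.

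**In the Statistical Analysis Plan**, state that the primary PaO₂ summaries and mixed model use only values drawn on 2 L/min. List the other values separately and give their number per arm. This does not remove the selection: the primary summaries will leave out patients who needed more oxygen and may overstate PaO₂. The count lets a reader judge by how much.

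Counts by time point, a note of desaturations that begin during sampling, and a worst-rank sensitivity analysis are optional.

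**Cost:** one added rule, device and flow fields for at most 20 × 4 = 80 draws, one short listing, and a few primary values set apart. The count is also a feasibility result in its own right, since it shows how often the primary endpoint can be measured as designed.
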